ATTACHMENT A- SURGEON PREFERENCE QUESTIONNAIRE (SPQ)**Instructions**

- This questionnaire is self-administered and should be completed by the surgeon prior to the first subject being implanted in the study.
- The purpose of this questionnaire is to collect your preferred toric IOL and its implantation volume.

1) Please specify your choice for preferred monofocal toric IOL (choose one).

TECNIS® Monofocal Toric
AcrySof® IQ Toric
enVista Toric
Other, Specify _____

2) Please specify your choice for preferred presbyopia-correcting toric IOL (choose one).

TECNIS Symfony® Toric
AcrySof® IQ ReSTOR®
AcrySof® IQ PanOptix®
Trulign Toric
Other, Specify _____

3) On average how many patients do you typically implant with your preferred monofocal toric IOL on a monthly basis?

Less than 5
5 to 10
11 to 15
More than 15
Other, Specify _____

4) On average how many patients do you typically implant with your preferred presbyopia-correcting toric IOL on a monthly basis?

Less than 5
5 to 10
11 to 15
More than 15
Other, Specify _____

ATTACHMENT B- SURGICAL HANDLEABILITY QUESTIONNAIRE (SHQ)**Instructions**

- This questionnaire is self-administered and should be completed by the surgeon following the completion of the surgery for each eye.
- The purpose of this questionnaire is to collect surgeon feedback on the handleability of the TECNIS® Toric II IOL (study lens).

Rate your level of confidence in controlling the position of the study lens in the implanted eye?

5- Extremely confident	
4- Quite a bit confident	
3- Somewhat confident	
2- A little confident	
1- Not at all confident	

If you answered “1-Not at all confident” or “2- A little confident”, please specify reason.

ATTACHMENT C- SURGEON SATISFACTION QUESTIONNARE (SSQ)**Instructions**

- This questionnaire is self-administered and should be completed following the completion of the last study visit (**3-month visit**) for each eye separately.
- The purpose of this questionnaire is to collect your feedback on the clinical outcomes achieved in each eye implanted with the TECNIS® Toric II IOL (study lens).

1) Please rate your overall level of satisfaction with the clinical outcomes achieved in the implanted eye.

5- Very satisfied	
4- Satisfied	
3- Undecided	
2- Dissatisfied	
1- Very dissatisfied	

If you marked “1- Very dissatisfied” or “2- Dissatisfied”, please specify reason.

2) Please rate your level of satisfaction with the rotational stability of the study lens in the implanted eye.

5- Very satisfied	
4- Satisfied	
3- Undecided	
2- Dissatisfied	
1- Very dissatisfied	

If you marked “1- Very dissatisfied” or “2- Dissatisfied”, please specify reason.

3) Please rate your level of satisfaction with the achieved uncorrected distance visual acuity in the implanted eye.

5- Very satisfied	
4- Satisfied	
3- Undecided	
2- Dissatisfied	
1- Very dissatisfied	

If you marked “1- Very dissatisfied” or “2- Dissatisfied”, please specify reason.

ATTACHMENT D- SURGEON OVERALL EXPERIENCE QUESTIONNARE (SEQ)**Instructions**

- This questionnaire is self-administered and should be completed after the last subject's 3-month visit for each surgeon at your site.
- Please answer the questions based on your overall experience with your preferred toric IOL prior to the study vs. TECNIS® Toric II IOL (study lens).

1. How is the rotational stability of the study lens in comparison to your preferred monofocal toric IOL used prior to the study?

5- Much better	
4- Somewhat better	
3- Same	
2- Somewhat worse	
1- Much worse	

If you answered "1- Much worse" or "2- Somewhat worse", please specify reason.

2. How is the rotational stability of the study lens in comparison to your preferred presbyopia-correcting toric IOL used prior to the study?

5- Much better	
4- Somewhat better	
3- Same	
2- Somewhat worse	
1- Much worse	

If you answered "1- Much worse" or "2- Somewhat worse", please specify reason.

3. Rate your level of confidence in treating astigmatism with the study lens in comparison to your preferred monofocal toric IOL used prior to the study?

5- Much more confident	
4- Somewhat more confident	
3- Same	
2- Somewhat less confident	
1- Much less confident	

If you answered "1-Much less confident" or "2- Somewhat less confident", please specify reason

4. Rate your level of confidence in treating astigmatism with the study lens in comparison to your preferred presbyopia-correcting toric IOL used prior to the study?

5- Much more confident
4- Somewhat more confident
3- Same
2- Somewhat less confident
1- Much less confident

If you answered “1-Much less confident” or “2- Somewhat less confident”, please specify reason

5. Would you recommend the study lens to your fellow surgeons?

3- Yes
2- Maybe
1- No

If you answered “1- No” or “2- Maybe”, please specify reason.

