9. INVESTIGATOR SELECTION

9.1 INVESTIGATOR QUALIFICATIONS

JJSV will select ophthalmic surgeons who have completed a residency in ophthalmology (or its documented equivalent) and are licensed to practice medicine and perform surgery at his/her investigative site. Each site will have one designated principal investigator; some sites may have additional sub-investigators performing surgery for study cases.

Investigators will be selected from surgeons who are experienced in small-incision, cataract extraction and toric IOL implantation in cataract patients. Surgeons are defined as professionals with experience in handling the surgical products and are familiar with the English language. All communication between the site and the sponsor will be in English. Additionally, surgeons should have established their personalized A-constant for the TECNIS® 1-Piece lens platform.

All sites will be required to have adequate staff support for reporting and patient follow-up, as well as the instrumentation necessary to conduct study testing.

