20.1 ANALYSIS POPULATION

For the primary endpoint, the primary analysis population will be all eyes implanted with a toric IOL (model ZCU150 through ZCU600) and with available data at the 3-month visit. For other endpoints, all eyes implanted with a toric IOL model ZCU150 to ZCU600 and with available data at the key timepoint for that endpoint will be used. In addition, data for the primary endpoint will also be evaluated by IOL model for lower-cylinder IOLs (ZCU150), medium-cylinder IOLs (ZCU225 to ZCU375) and for extended higher-cylinder IOLs (ZCU450, ZCU525 and ZCU600). For the surgeon preference questionnaire (SPQ) and the surgeon experience questionnaire (SEQ), the analysis population will be surgeons responding to these questionnaires.

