20.3 OTHER ENDPOINTS

For other items on the SSQ, the frequency and proportion of eyes with each response will be reported for the individual items on the questionnaire. The frequency and proportion of eyes will be reported for the single-item on the SHQ. For the SEQ and the SPQ, the frequency and proportion of surgeons with each response will be reported.

Descriptive statistics for all eyes will be reported for mean refractive cylinder, cylinder vs intended cylinder, spherical equivalent and spherical equivalent vs intended and for percent reduction in cylinder. In addition, the frequency and proportion of eyes within 0.50 D and within 1.00 D of intended values will be reported for refractive cylinder and spherical equivalent.

For visual acuity, the values will be converted to logMAR prior to analysis. Descriptive statistics for all eyes will be reported for mean logMAR monocular uncorrected and best corrected distance visual acuity. The frequency and proportion of eyes achieving each acuity line will also be reported for uncorrected and best corrected distance visual acuity.

Enrollment data, demographic data, accountability data and operative complications/procedures will be reported using descriptive statistics.

The frequency and proportion of eyes with medical/lens findings or adverse events will also be reported.

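### SEQ items 2 and 4 offer no 'not applicable' answer to surgeons without a presbyopia-correcting toric lens, and Section 20 has no rule for counting their ratings

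*Combined protocol and SAP*

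**What the plan says.** Attachment D, SEQ item 2, asks "How is the rotational stability of the study lens in comparison to your preferred presbyopia-correcting toric IOL used prior to the study" and item 4 asks "Rate your level of confidence in treating astigmatism with the study lens in comparison to your preferred presbyopia-correcting toric IOL used prior to the study". Each is followed by five ratings from most to least favourable. Neither has a 'not applicable' box or a skip instruction. A written reason is requested only for the two unfavourable ratings.

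Section 9.1 sets the surgeon requirement: "Investigators will be selected from surgeons who are experienced in small-incision, cataract extraction and toric IOL implantation in cataract patients". It does not mention presbyopia-correcting toric lenses.

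Attachment A, the SPQ completed before a surgeon's first study implant, has two relevant items:

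- Item 2: "Please specify your choice for preferred presbyopia-correcting toric IOL (choose one", with four named lenses and 'Other, Specify'. There is no 'none'.
- Item 4: "On average how many patients do you typically implant with your preferred presbyopia-correcting toric IOL on a monthly basis". The lowest band is 'Less than 5', with no separate zero. 'Other, Specify' is offered here too.

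For both questionnaires, Section 20.1 says "the analysis population will be surgeons responding to these questionnaires". Section 20.3 adds: "For the SEQ and the SPQ, the frequency and proportion of surgeons with each response will be reported". Neither section gives an item-level denominator, a rule for blank items, or a link from a surgeon's SPQ answers to that surgeon's SEQ answers.

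**The concern.** Items 2 and 4 make sense only for a surgeon who used a presbyopia-correcting toric lens before the study. The selection criteria admit surgeons who did not. Such a surgeon can leave the item blank or tick a rating, and the plan deals with neither case. A tick enters the proportion as if it were a comparison. A blank may or may not stay in the denominator.

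'Same' is also the neutral answer and needs no explanation, so it is an easy choice for someone with nothing to compare. Afterwards, the analyst could not reliably tell that tick from a user's considered judgement that the two lenses perform alike. At stake is whether the two percentages can be read as what they purport to be: the view of surgeons who have used both kinds of lens.

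**Working it through.** **The plan's own figure.** The documents state no figure for the SEQ. The only stated precision is in Section 20.4, for the primary endpoint: within 1.4% for 1000 eyes at 95%. The Wald half-width is 1.96 × √(0.95 × 0.05 / 1000) = 0.0135, or 1.35 points, which rounds to 1.4. It reproduces, and nothing in this point alters it.

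**Can non-users be present, and can they be found?**

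1. Entry: Section 9.1 requires toric experience in general, so a surgeon who implants only monofocal toric lenses qualifies.
2. SPQ item 2: a non-user can be recognised only by writing something like 'none' under 'Other, Specify', or by leaving the item blank. Neither is prompted.
3. SPQ item 4: a non-user who ticks the lowest band looks the same as a surgeon implanting 1 to 4 a month.
4. SEQ items 2 and 4: no answer declares non-use.
5. Sections 20.1 and 20.3: the population is defined by response to the questionnaire, not by item or by use of the comparator.

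**Illustration of size.** All inputs here are assumptions except the order of magnitude of 50, which comes from the maximum of 50 sites. The number of surgeons is not stated, and Section 9.1 allows sub-investigators, so it could be higher. Let *t* be the share of users who give a favourable rating ('better' on item 2, 'more confident' on item 4) and *f* the share of surgeons who are non-users.

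- Non-users all mark 'Same', or are blank but kept in the denominator: reported share = *t*(1 − *f*).
- Non-users all mark a favourable rating: reported share = *t*(1 − *f*) + *f*.
- Users-only denominator: *t*.

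With *t* = 60% and 50 surgeons:

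| *f* | users | favourable users | users only | non-users 'Same' | non-users favourable |
|---|---|---|---|---|---|
| 10% | 45 | 27 | 60% | 27/50 = 54% | 32/50 = 64% |
| 20% | 40 | 24 | 60% | 24/50 = 48% | 34/50 = 68% |
| 30% | 35 | 21 | 60% | 21/50 = 42% | 36/50 = 72% |

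With *t* = 80% and the same three values of *f*, the 'Same' column becomes 72%, 64% and 56%, and the favourable column 82%, 84% and 86%.

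**Scale against sampling error.** For 50 surgeons at 60%, the 95% Wald half-width is 1.96 × √(0.6 × 0.4 / 50) = 0.136, or 13.6 points. The downward shifts of 6 and 12 points lie inside that; the shift of 18 points exceeds it. Unlike sampling error, this shift would not shrink with more surgeons.

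**The case against.** The strongest reply has four parts.

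- **Nothing compels an answer.** The SEQ is self-administered and no text makes an item mandatory, so a non-user may skip it. This stands, and a reader who inferred that the form forces a rating would be going beyond the documents. It does not settle the matter, because the plan does not say how a blank is counted. Section 15.1 also plans checks to reduce omissions; whether they cover the SEQ is not stated.
- **The SPQ has a write-in.** A surgeon can enter 'none' or '0' under 'Other, Specify', and the SPQ is collected from each surgeon, so matching it to the SEQ looks feasible. This also stands: it would be wrong to say that non-users can never be identified. But the write-in is unprompted and no planned analysis uses it, so identification is not reliable.
- **No non-user has been shown to exist.** This is correct. The documents neither report nor exclude any, and if every surgeon had used such a lens there would be no bias.
- **The consequence is small.** These are two of five SEQ items within one of seven other endpoints, reported descriptively with no test or success threshold. This stands in full and limits the weight of the point.

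**Conclusion.** The gap is real but narrow. SEQ items 2 and 4 ask for a comparison that an eligible surgeon may be unable to make. The forms do not reliably separate those surgeons, and Section 20 has no rule that does. Any rating they give would be reported as a genuine comparison.

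The size and sign of the effect cannot be determined from the documents. The illustrated figures depend on an assumed non-user share, an assumed true value and an assumed answering pattern. A reader might infer from the 'Same' scenario that the study lens will be under-rated. The documents do not support that: non-users who carry over a good opinion formed against a monofocal lens would push the figure up. Nor do they support calling the SEQ as a whole compromised. Items 1, 3 and 5, the primary SSQ endpoint and the sample size are untouched.

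The change is worth making because it is inexpensive and, without it, these two percentages cannot be read as the judgement of surgeons who used both lenses.

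**What to change.** 1. **SEQ items 2 and 4:** add a box reading 'Not applicable - none used before the study'. This is sufficient alone, because the SEQ is completed after each surgeon's last 3-month visit and so also reaches surgeons who have already filled in the SPQ.
2. **Section 20.1:** state that the denominator for SEQ items 2 and 4 is surgeons who used a presbyopia-correcting toric IOL before the study, with the not-applicable and blank counts reported separately.
3. **Optional, for surgeons who have not yet completed the SPQ:** add 'None' to item 2 and a separate '0' band to item 4.

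**Cost.** This is a minor form amendment. Under Section 12 it needs approval by the IRB(s), and by regulatory agencies as appropriate, before use at up to 50 sites. The denominator for the two items becomes smaller, so their percentages are less precise.

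If the form cannot be changed, a weaker fallback is to report each item with its own number of respondents and to list blanks and any SPQ write-ins indicating non-use. That catches only surgeons who skipped the item or volunteered the information.
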